3 OBJECTIVES AND OUTCOME MEASURES/ENDPOINTS

To establish that the DC Mobile can be used in a supported accommodation environment to record and retrospectively detect changes in chest movement consistent with respiratory patterns of an accidental drug overdose.

3.1 Table of endpoints/outcomes

Objectives	Outcome Measures	Timepoint(s) of evaluation of this outcome measure (if applicable)
Primary Objective To capture chest motion data using the PneumoWave DC Mobile system	Evidence reduced chest movement using PW DC Mobile system.	End of study
Secondary Objectives Usability and functionality of the DC Mobile biosensor	Participant reported satisfaction survey, feasibility questionnaire, semi-structured interviews, focus group	Day 0 to end of study
Secondary Objectives Potential SIRD events linked to participant drug use behaviour or existing respiratory condition. Substance use and staff-measured outcomes (including overdose) by attendees of supported accommodation	AIR tool questionnaire, drug use diary, CRF	Day 0 to end of study

[figure not shown]
4 STUDY DESIGN

This is an observational study. It will not incorporate any randomisation or intervention. Participants' health care and the management of any potential SIRD event will not be altered by the procedures of the protocol.

People who use drugs often live in supported accommodation, either for short periods or over a period of years. Many may continue to use drugs while on these premises. To stay at these premises people must be registered as a resident. Short term residents must register before they take up accommodation. Potential participants will be opportunistically recruited by staff working in these premises who are trained to fully explain the study and take informed consent. Drug use is discussed with residents for their own safety. Accommodation staff engage regularly with this population and will be able to identify those who may be eligible. This lowers the risk of them approaching people who do not use drugs and potentially causing unintentional offence or stereotyping. Some supported accommodations will provide injecting equipment on request. This would identify a potentially eligible participant. Consented participants will be recorded on an enrolment log at each participating site. The enrolment log is for administration purposes only and will only be available to site personnel.

The study will utilise the PneumoWave DC Mobile biosensor and data collection platform which includes a wearable biosensor that attaches to the press-stud on a supplied and approved ECG electrode. The biosensor can be placed in a number of locations on the chest and diaphragm area, and automatically connects to a Data Hub via Bluetooth (Fig. 1). The position of the biosensor should be changed weekly. In this study the Hub will be a mobile computing platform (Application running on a tablet). The tablet will be held in a secure location, remaining in range of connection for the PneumoWave DC Mobile biosensor. The tablet has no functionality beyond running the monitoring app. Participants will be informed of this and the tablet's location in their residence. Please see further details in the Study Assessments section (section 7.4).

Figure 1:

Participants receive the device to wear and a tablet with the DC Mobile app downloaded to record data while they are in their accommodation. The wearable device battery will be changed 1-2 times per week.

Long term residents: monitored for 4 weeks or longer up to 8 months

Supported accommodation staff will check in weekly with participants to ensure the device is being worn, is working and the associated tablet is also present and in a working condition. Participants will receive £25 per week if these conditions are met (further detailed in Payment section). This will encourage participants to look after the device and tablet as only a limited number of each will be available at each site. Site staff will check in on participants overnight to check the device is being

worn and the app is running and note any potential drug use. Participants will be asked to wear the device for 4 weeks initially, with an option to extend the period, if agreed. This continues until the participant declines to be part of the study any longer or the study end point is reached, whichever is first.

Short term residents: monitored overnight

Participants will receive the biosensor and tablet to use overnight and return in the morning. They will receive £5 for returning both the biosensor and device in the morning. Up to a maximum of £25. If they remain a resident, they will recollect the biosensor and tablet for all nights that they are resident. This continues until the participant declines to be part of the study any longer or the study end point is reached, whichever is first. Site staff will be trained to ask for ongoing consent if there are three or more nights where the participant has not been resident at the supported accommodation, following initial informed consent. Site staff will check in on participants to check the device is being worn and the app is running and note any potential drug use.

Applicable to all residents/participants:

It is not expected that participants will always be at a participating site. When leaving the site, the biosensor should be left behind along with the tablet. The biosensor can continue to collect chest movement data while out of range of the tablet for 10-12 hours, once back in range, data will automatically be sent to the tablet. A light on the biosensor will flash red for the duration of time it is out of range.

During their stay at the supported accommodation, participants will be asked to complete a questionnaire on device feasibility and a satisfaction survey at least once on how they felt about wearing the device. Participants who remain at the site longer may complete the survey more than once to record fluctuating levels of acceptance. During study registration, participants will be asked to complete an AIR tool, which captures the participants' injecting habits over the previous 6 months. They will also be asked to complete a drug use diary. A sub-section of participants will be asked to take part in semi-structured interviews and/or focus groups to discuss wearing the device, ease of use and to help determine any other potential issues with the device or software.

Staff participants:

Staff participants will be asked to complete a study questionnaire at least once during the study to indicate their satisfaction with the PneumoWave DC Mobile biosensor. This may be completed more than once to capture changing opinion.

Some staff will be invited to take part in a semi-structured interview and/or focus group to discuss their experience with the PneumoWave DC Mobile biosensor.

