6.2 Exclusion criteria

- Does not meet one or more of the inclusion criteria
- Skin sensitivity to ECG electrode patch
- Broken skin over chest area
- Implanted pacemaker device in-situ
- Not suitable for enrolment in opinion of site staff or investigators

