7.1.3 Payment

Long term resident participants will receive £25 per week dependent on evidence of wearing the biosensor and the tablet remaining in situ in their residence.

Short term participants will receive £5 for returning the biosensor and tablet the morning after use. Up to a maximum of £25.

Participants will receive £20 for taking part in semi-structured interview and £10 for participation in a focus group.

To avoid supported accommodation keeping physical money on-site, where possible participant payments will be made using the Cash Out system (<https://tinyurl.com/mr9c75kn>). This involves the supported accommodation staff sending a text message to the participant, stating the cash value to be received. This text message can be presented at any PayPoint location and the participant will receive the cash value. If a participant does not have a mobile telephone, arrangements will be made to provide the participant with the cash sum or a shopping voucher of the corresponding value.

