7.6 Withdrawal criteria

Participants are free to withdraw at any time and are not obliged to give reason(s). The CI, PI or delegate will make a reasonable effort to ascertain the reason(s), both for those who express their right to withdraw and for those lost to follow up, while fully respecting the individual's rights. The investigator may withdraw a participant at any time if it is in the best interest of the participant and continuation in the study would be detrimental to the participant's wellbeing. A full explanation will be provided in these instances.

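### The long term residents' £25 weekly payment has two different conditions, and neither makes an exception for stopping wear because of a skin problem

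*Protocol*

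**What the plan says.** Protocol section 4, long term residents: site staff check in weekly "to ensure the device is being worn, is working and the associated tablet is also present and in a working condition". It continues: "Participants will receive £25 per week if these conditions are met (further detailed in Payment section)". The stated purpose is care of the equipment: "This will encourage participants to look after the device and tablet as only a limited number of each will be available at each site".

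Protocol section 7.1.3 pays the same £25 "dependent on evidence of wearing the biosensor and the tablet remaining in situ in their residence". It does not require the sensor or the tablet to be working.

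Short term residents are paid £5 for bringing the sensor and tablet back in the morning, up to £25 (sections 4 and 7.1.3). Neither wear nor function is a condition for them.

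Section 6.2 excludes at entry anyone with "Skin sensitivity to ECG electrode patch" or "Broken skin over chest area". Section 7.6 lets participants leave freely and adds: "The investigator may withdraw a participant at any time if it is in the best interest of the participant", where continuing would harm their wellbeing. It does not mention payment, or an entry exclusion that appears after enrolment.

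**The concern.** The two sections give different answers to the same question: is a resident paid for a week in which the sensor or tablet has failed? Four organisations manage the sites (section 5) and no formal monitoring is planned (section 12), so sites could apply different rules. Informal site discretion is a weak remedy, because section 13.5 does not allow planned deviations or waivers.

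The skin problem arises under both sections. A resident who takes the sensor off because the skin has reacted no longer meets the wear condition, and no exception is written. That person might be ineligible under section 6.2 if assessed for entry that day, yet the payment rule favours keeping the sensor on.

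Two things are at stake. One is participant safety: a payment that works, however mildly, against stopping for a device-related problem. The other is the completeness of an outcome. Section 9.3 makes adverse events related to wearing the device a study outcome, and section 9.4 has the research team identify adverse events from what participants say in the CRF or in interviews. That route depends on disclosure.

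**Working it through.** The protocol gives no figure to reproduce on this point. The check compares the two payment rules case by case, read literally.

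| Situation at the weekly check (long term resident) | Section 4 | Section 7.1.3 |
|---|---|---|
| Sensor worn and working, tablet present and working | Paid | Paid |
| Sensor worn, but sensor or tablet has failed; tablet in place | Not paid | Paid |
| Sensor off all week because of a skin problem; tablet in place | Not paid | Not paid |
| Sensor worn part of the week, then off because of a skin problem | Not paid if off at the check | Unclear: turns on what counts as evidence of wear |

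1. Row 2 is the contradiction. Section 7.1.3 drops the two function tests that section 4 applies. One qualification: section 8.4 assesses compliance from downloaded data. If those data were the evidence of wear, a failed sensor could cost the payment under section 7.1.3 too, but the protocol does not say so.
2. Row 3 is the skin problem. Both sections give the same answer, and neither states an exception.
3. Row 4 shows that the loss is not automatic. Section 4 also tells participants to leave the sensor behind when they go out, so continuous wear is not what is being paid for.

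Money tied to the condition:
- Per affected week: £25 (sections 4 and 7.1.3).
- Initial period of 4 weeks (section 4): 4 × £25 = £100.
- Ceiling for the longest monitoring in section 4, 8 months: 8/12 × 365.25 / 7 ≈ 34.8 weeks, so 34 full weeks × £25 = £850. This would need the condition to fail every week, so it is a bound and not an expectation.

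Past exposure (section 2.1): over 150 participants and 15,000 hours of wear with no biosensor-related adverse events. 15,000 / 150 = about 100 hours each on average. Under an assumed 8 to 12 hours of wear a night, four weeks is 28 × 8 = 224 to 28 × 12 = 336 hours. The earlier record is reassuring, but on that assumption it reflects shorter average wear than is planned here.

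**The case against.** The case on the other side is substantial, and much of it stands.

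- **Section 4 defers to the Payment section.** Section 7.1.3 is then the natural operative rule, and under it a fault does not cost the payment. The stated purpose in section 4 is care of equipment, not penalising spontaneous failure. This weakens the point about faults. It does not remove the need to align two sections that name different conditions.
- **Faults are hard to hide.** A reader might infer that the rule suppresses the device failures the study is meant to find and so biases the usability and functionality objective. The protocol does not support that. Staff check function weekly and look overnight at whether the app is running (section 4); downloaded data show compliance (section 8.4); staff complete their own questionnaires (section 4); and interviews and focus groups are paid separately at £20 and £10 with no wear condition (section 7.1.3).
- **Payment may not stop.** A reader might also infer that a participant is paid only if the sensor stays on throughout, or is driven out of the study by lost payment. Evidence of wear is not continuous wear, the protocol nowhere expressly says that payment is withheld in these cases, and the participant information sheet is not at hand.
- **Skin problems are partly provided for.** The sensor can go in several places and is to be moved weekly (section 4), and section 7.6 gives a general best-interest power to withdraw. Both may reduce the problem. Neither changes the payment rule or says what applies when an entry exclusion arises during wear.

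What remains is the inconsistency, and the missing exception for skin problems.

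**Conclusion.** The point holds in a limited form. Sections 4 and 7.1.3 state different conditions for the same payment and must be reconciled. Taken literally, both make payment depend on wear without an exception for a skin problem of a kind that bars entry, and section 4 alone would also withhold payment for a fault the participant did not cause.

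The consequence is a modest incentive against stopping for, or disclosing, a device-related skin problem. Any effect on the recording of faults is small, because staff check function directly. The sum is £25 per affected week, up to £100 over the first four weeks. How many residents would be affected cannot be estimated: the protocol gives neither the number of long term residents nor a rate of skin problems or faults.

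The conclusion rests on inferring loss of payment from conditional wording with no exception, and on the information sheet not adding one. It is worth correcting because the correction is cheap, not because the results are threatened.

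**What to change.** 1. State one payment condition, in the same words, in sections 4 and 7.1.3. Keep the wear and equipment-care requirements. Paying simply for keeping the equipment and attending the check would remove the incentive to wear the sensor for everyone, and capturing chest motion data is the primary objective.
2. Add that payment is not withheld for a week in which the sensor is off or not working because of a reported skin problem, or because of a device or tablet fault confirmed at the weekly check.
3. Record on the CRF the date and reason whenever wear stops (skin, fault, own choice), and report stopping by reason. The CRF content listed in section 11.1 covers issue and return of the equipment but names no reason for stopping. Participants remain free not to give one (section 7.6).
4. Reconcile sections 6.2 and 7.6 on what applies when an entry exclusion arises during wear. The content of that rule is for the investigators.

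Cost: a few extra £25 payments, one CRF field and a protocol amendment. There is a small risk of false claims, which staff can verify at the weekly check they already make.

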2.1 Assessment and management of risk

There is zero to minimal risk to participants from the biosensor itself. It may be mildly uncomfortable to wear initially but participants should soon become used to it. Several Clinical Research projects have been conducted with the technology (eg. *RESCU: RESpiratory monitoring reduCing drUg harm*, IRAS 301153) with over 150 participants and 15,000 hours of wear. No adverse events related to the biosensor have been reported.

There is no risk of personal data being revealed via the DC Mobile software. All chest movement data is anonymous.

Participants are people who actively use drugs and may be at risk of accidental overdose. Supported accommodation sites involved in the study have trained staff to administer naloxone, to reverse the effects of an opioid overdose or to administer first aid. Participants will be informed that the device will not issue an alert in the event of a potential overdose. Supported accommodation staff perform regular wellness checks on residents who show signs of drug use throughout the evening. Staff will continue to perform these checks on study participants, so there is no change to the risk of accidental overdose.

Sites provide advice and additional services to help residents stop using opiates and other drugs. Participants will not be disincentivised from using these services.

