7.4 Study assessments

Participants will answer questions to determine their demographics such as age, BMI and gender at birth. If required, participant will be weighed and measured to calculate their BMI. Participants will be asked if they have any existing respiratory medical conditions. After wearing the biosensor, participants will complete a short satisfaction survey on their experience of PneumoWave DC. Participants should complete this at least once. Participants who stay at the site for a longer period may complete more than one to show fluctuating levels of acceptance. Participants will be asked to complete a drug use diary and an AIR tool to describe their drug use. Drug use and care is discussed with participants so these can be completed in the presence of and with support of, site staff.

During welfare checks, site staff will record any evidence of drug use in the pCRF. If a participant requires intervention due to a potential overdose event, site staff will record this in the pCRF, along with the level of intervention required, if the participant is unresponsive. Where possible the biosensor will be left on the participant during the intervention, and removed once the participant has sufficiently recovered or prior to leaving the facility (i.e. transfer to a medical facility).

A subsection of participants will be asked to partake in semi-structured interviews, lasting no longer than 60 minutes, to describe their experience wearing the device.

A further subsection of participants, including those who may have had an interview, will be asked to take part in focus groups to discuss the PneumoWave DC Mobile and the prototype for the Alert system and the perceived benefits or downsides it may have.

Staff from across all participating supported accommodation will be invited to take part in a semi-structured interview and/or a focus group to discuss their views on, perceived benefits of or barrier to use of the biosensor and DC Mobile system.

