8.4 Assessment of compliance with treatment

Compliance will be assessed by the downloading of anonymous respiratory patterns from devices that are returned by participants after use.

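### The protocol provides no record of wear status, check times or negative checks, so sensitivity and specificity cannot be confined to worn, verified time

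*Protocol*

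**What the plan says.** **Wear.** Protocol section 4, for all participants: "When leaving the site, the biosensor should be left behind along with the tablet". The next sentence describes a different situation: "The biosensor can continue to collect chest movement data while out of range of the tablet for 10-12 hours". Neither says that recording is paused or flagged when the sensor is taken off.

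**Checks.** For long-term residents, section 4 states: "Supported accommodation staff will check in weekly with participants to ensure the device is being worn, is working". For long-term residents overnight, and for short-term residents during their stay, staff also look in to see that the device is being "worn and the app is running and note any potential drug use". Section 2.1 describes the sites' routine practice: "Supported accommodation staff perform regular wellness checks on residents who show signs of drug use throughout the evening".

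**Records.** Section 7.4: "During welfare checks, site staff will record any evidence of drug use in the pCRF". On overdose: "If a participant requires intervention due to a potential overdose event, site staff will record this in the pCRF". Section 11.1 adds potential respiratory depression events with their outcomes, and the issue and return of sensor and tablet.

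**Analysis.** Section 10.3.2 compares whether an alarm would have been raised with a review of staff-measured outcomes, then calculates sensitivity and specificity over the whole data set. Section 10.4 reconciles sensor data with staff and participant reports and drops what does not match.

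**Compliance.** Section 8.4: "Compliance will be assessed by the downloading of anonymous respiratory patterns from devices that are returned by participants after use".

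**The concern.** Sensitivity and specificity need, for each period analysed, a sensor result from a worn sensor and a reference result that someone actually established. Section 2 accepts this: it wants chest motion captured where both the occurrence and the non-occurrence of overdose can be confirmed from outside.

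The records that the protocol lists are almost all positive findings. If a check finds the participant well and the sensor in place, no section says that this is written down. If the participant is out and the sensor is on a table, no section says that this is written down either. In the data, three situations then look alike: a participant checked and well, a participant not checked, and a participant not wearing the sensor. All three can be scored as having no staff concern.

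Section 2 says the data will be used to test and further develop the breathing signatures for overdose, so unverified labels would affect the algorithm's development as well as the accuracy figures. A wear-time rule can reasonably be left to the SAP, and its absence from the protocol is no fault. But a SAP cannot recreate a check result that was never recorded.

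**Working it through.** The protocol states no accuracy figure, event rate or wear time, so there is nothing to reproduce. The inputs below are assumptions that show direction and size only.

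**1. Unworn time in the non-event windows.** Let Sp be the true specificity in worn time and u the share of non-event windows in which the sensor is unworn.
- If every unworn window alarms: apparent specificity = (1 − u) × Sp.
- If no unworn window alarms: apparent specificity = (1 − u) × Sp + u.

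With Sp = 90%:

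| u | all unworn windows alarm | none alarms |
|---|---|---|
| 5% | 85.5% | 90.5% |
| 10% | 81.0% | 91.0% |
| 25% | 67.5% | 92.5% |
| 40% | 54.0% | 94.0% |

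At u = 25%: 0.75 × 0.90 = 0.675, and 0.675 + 0.25 = 0.925. Restricting to worn time returns 90%.

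**2. Events that staff do not see.** Assume events in 2% of windows, sensitivity 80% and specificity 90%. Let v1 be the share of alarming events that staff observe and v0 the share of non-alarming events that they observe. An unobserved event is scored as no concern, so it moves from true positive to false positive, or from false negative to true negative.
- v1 = v0 = 60%: TP = 0.02 × 0.8 × 0.6 = 0.0096; FN = 0.02 × 0.2 × 0.6 = 0.0024; sensitivity = 0.0096/0.0120 = 80%. FP = 0.98 × 0.1 + 0.02 × 0.8 × 0.4 = 0.1044; TN = 0.98 × 0.9 + 0.02 × 0.2 × 0.4 = 0.8836; specificity = 0.8836/0.9880 = 89.4%.
- v1 = 90%, v0 = 50%: TP = 0.0144; FN = 0.0020; sensitivity = 0.0144/0.0164 = 87.8%.
- v1 = 90%, v0 = 30%: TP = 0.0144; FN = 0.0012; sensitivity = 0.0144/0.0156 = 92.3%.

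Incomplete observation therefore distorts sensitivity when events that trip the algorithm are also the ones that staff are more likely to notice. The listed records give no way to estimate v1 or v0.

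**3. The mismatch rule in section 10.4.** Take 1,000 non-event windows, 250 of them unworn, with Sp = 90% in the other 750.
- All unworn windows alarm: FP = 75 + 250 = 325; TN = 675; specificity 67.5%. Drop every sensor–staff mismatch and FP = 0, so specificity = 675/675 = 100%.
- None alarms: FP = 75; TN = 675 + 250 = 925; specificity 92.5%. Drop mismatches and it is 925/925 = 100%, with 250/925 = 27% of the true negatives coming from an unworn sensor.

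A false positive or a false negative is by definition a disagreement between sensor and staff. (Section 10.3.2 names true positives twice; I read one as false negatives.) Read literally, the rule sends both measures to 100% whatever the true values, and it keeps the unworn quiet windows because they agree with the absence of a staff note.

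**The case against.** **Staff do check wear.** They do, and not only on residents who show signs of drug use: the study checks in section 4 cover long-term and short-term participants. It would be wrong to say that quiet residents go unchecked. What stands is that no section says the result or time of such a check is recorded. Issue and return records bound the overnight period for short-term residents, but they do not show wear within it and help little for residents who keep the device for weeks. The case report form itself is not at hand, so the finding is about what the protocol provides for, not about what the form contains.

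**Section 10.4 may remove unworn alarms.** It may, so one cannot say that they will be counted as false positives. If the rule is meant only for linkage errors in identity or date, it leaves unworn time in. If it is meant literally, it removes genuine errors too. Neither reading isolates worn, verified time.

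**A reader might infer that unworn time inflates false alarms.** The documents do not support a direction. The Alert algorithm is proprietary and undescribed, and it may or may not ignore a motionless sensor.

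**A reader might infer that compliance is overstated because lost devices drop out.** This is not shown either. Section 2 says data are streamed to a cloud, so an unreturned device need not lose its data, and wear is also checked weekly and tied to payment. The wording of section 8.4 is narrow, but no overstatement follows.

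**The two sentences on leaving the site are not a strict contradiction.** One is an instruction and the other a device capability, and a participant could be out of range while still on the premises. They need clarifying.

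**Conclusion.** The point holds as a gap in data collection combined with two analysis rules that do not fit together. As written, unworn or unobserved time cannot be reliably separated from worn, verified time, and silence from staff can count as a true negative. Section 10.3.2 (use all data) and section 10.4 (drop mismatches) must be reconciled, and neither solves the problem.

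The size is illustrative. With an assumed 90% specificity and 25% unworn windows, apparent specificity lies between 67.5% and 92.5% according to how the algorithm treats a motionless sensor, and a literal mismatch exclusion gives 100%. The protocol gives no figure for absences, wear time or overdose events, so a count of non-wear episodes, or a ratio of such episodes to true events, cannot be derived from it.

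This should be changed while data are still being collected, because the missing records cannot be recovered afterwards.

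**What to change.** 1. **Sections 4, 7.4 and 11.1.** At the checks staff already make, record clock time, sensor worn (yes/no), and no concern / concern / intervention, with negative checks entered as well.
2. **Sections 10.3.2 and 10.4.** Replace the use of all data and the mismatch exclusion with a definition of analysable time. It should be (a) worn, by a non-wear rule fixed before sensor and staff data are linked and blind to the staff outcome, and (b) covered by a timed check within a fixed window. Both are decided without regard to whether sensor and staff agree. Section 1 describes overdose as progressing to complete loss of respiratory effort, so the non-wear rule should be tested against the recorded wear status, lest it discard true events as unworn time.
3. **Remaining time.** Tabulate alarms and quiet periods outside analysable time separately as unverified, not as false positives or true negatives.
4. **Section 4.** Clarify how the instruction to leave the sensor behind relates to the sentence on out-of-range collection, and say how unworn recording is marked.
5. **Section 8.4.** Compute compliance from the cloud data over all issued participant-nights, not only from returned devices.

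**Cost.** Three fields and a few seconds per check, plus analysis wording. The checks are intermittent, so a possibly substantial share of recorded time will be classed as unverified. Participants' care does not change.
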